1. PROTOCOL SUMMARY

1.1. SYNOPSIS

Study Population:	This study will enroll male and non-pregnant female ≥ 20 years of age with healthy subjects. Totally 30 subjects will be hospitalized and enrolled in this study.
Phase:	I
Description of Study Intervention:	CX-4945 will be administered at 200mg QD, 200mg BID or 400mg BID for continuously 5 days.
Study Duration:	5 months (from study initiation until completion of data analyses)
Subject Duration:	The total duration of the treatment will be 5 days. Subjects will be followed up at 14 days from the start of the treatment.

1.2. SCHEMA

1.3. SCHEDULE OF ACTIVITIES (SOA)

Table 1: Schedule of Activities

Procedure/Assessments	Screening Visit	Treatment				Follow-Up
Day	SV Day -28~ 0	Day 1 (Baseline)	Day 3	Day 5	Day 6 (EOT)	Day 14
Window Period		within 28 days after SV				±3 days
Informed Consent [1]	X					
Eligibility Evaluation [2]	X					
Subject Demographics	X					
Medical History [3]	X					
Physical Examination	X	X	X	X	X	X
Weight and Height	X					
Vital Signs [4]	X	X	X	X	X	X
ECG	X	X	X	X	X	
Laboratory Tests:	X	X	X	X	X	X
Hematology [5]	X	X	X	X	X	X
Blood Biochemistry [6]	X	X	X	X	X	X
Coagulation [7]	X	X	X	X	X	X
Serum/Urine Pregnancy Test [8]	X	X				X
Urinalysis [9]	X	X	X	X	X	X
Anti-HIV, Anti-HBV, Anti-HCV	X					
Anti-SARS-CoV2 [10]		X				
IP Administration		CX-4945 200 mg QD daily (Day 1 to Day5) CX-4945 200 mg BID daily (Day 1 to Day5) CX-4945 400 mg BID daily (Day 1 to Day5)				
Concomitant Medications	X	X	X	X	X	X

Adverse Events		X	X	X	X	X
----------------	--	---	---	---	---	---

[1] Informed consent must be obtained prior to subject participation in any protocol-related activities that are not part of routine care.

[2] Initial evaluation of subject eligibility will be performed by Investigator. Subject number will be assigned on Day1 after confirming the subject eligibility.

[3] Medical history and current therapies (medications and non-medications).

[4] Vital signs will include blood pressure, heart rate, respiration rate, SpO₂, and temperature.

[5] Hematology: Hemoglobin, Hematocrit (HCT), Red Blood Cells (RBC), White Blood Cells (WBC) with total, differential count,(Absolute Neutrophil Count, Absolute Lymphocytes Count, Absolute Monocytes Count, Absolute Eosinophils Count, Absolute Basophils Count) and platelets.

[6] Blood biochemistry:

- Hepatic function indicators: total bilirubin, alkaline phosphatase (ALP), aspartate aminotransferase (AST), alanine aminotransferase (ALT), total protein, albumin, lactate dehydrogenase (LDH)
- Renal function indicators: BUN, Serum creatinine
- Electrolytes: sodium, potassium, chloride, magnesium, phosphorus, total calcium and bicarbonate,
- Other: Creatine phosphokinase (CPK), C-reactive protein (CRP), Creatine kinase-MB(CK-MB mass), Triglyceride, Total Cholesterol, Glucose AC, Uric Acid, γ -GT.

[7] Coagulation: Prothrombin time (PT) and International Normalized Ratio (INR)

[8] ONLY performed on women of childbearing potential. Pregnancy Test will be tested on screening, Day 1 prior dosing and Day 14.

[figure not shown]
[9] Urine samples will be tested for color, appearance, specific gravity, pH, protein, glucose, occult blood, ketones, leukocyte esterase, nitrite, bilirubin, urobilinogen, and microscopic examination of urine sediment.

[10] In response to the COVID-19 pandemic, the subject will need to follow the currently site's policies for COVID-19 to get the negative results of anti-SARS-Cov2 test before admission.

[figure not shown]
2. INTRODUCTION AND BACKGROUND

2.1. STUDY RATIONALE

The COVID-19 pandemic is an ongoing global pandemic caused by severe acute respiratory syndrome coronavirus 2 (SARS-CoV-2). It was first identified in December 2019 in Wuhan, China. As of 28 July 2022, more than 573 million cases have been confirmed, with more than 6.39 million deaths attributed to COVID-19. Symptoms of COVID-19 are highly variable, ranging from none to life-threatening illness. The virus spreads mainly through the air from person to person. Common symptoms include headache, loss of smell and taste, nasal congestion and rhinorrhea, cough, muscle pain, sore throat, fever, diarrhea, and breathing difficulties. Most people develop mild to moderate symptoms.

Protein kinase, CK2, is a constitutively active serine/threonine kinase which has been studied as a pro-survival, anti-apoptotic kinase. Overexpression of CK2 has been reported in multiple cancers and shown to be linked to disease progression and poor prognosis. CK2 plays a crucial role in multiple non-oncogenic processes required to sustain the cancer phenotype, including the Hedgehog (Hh) pathway. Apart from oncology diseases, overexpression of CK2 has also been observed in some auto-immune and inflammatory diseases *in vivo*, and viral infections.

Understanding the safety and efficacy of CX-4945 will be the key of targeted COVID-19 therapies that can be used against the activated CK2 kinase signaling pathway in COVID-19.

2.3. OVERALL RISK AND BENEFIT ASSESSMENT

In the context of complications potentially associated with SARS-CoV-2 virus infection and the limitation of effective preventative measures in COVID-19 epidemics, the established pre-clinical toxicological profiles and mechanism of action of CX-4945 supports a favorable benefit/risk relationship of the product. This favorable relationship should translate into improved compliance

and offers an alternative program for mild to moderate COVID-19 treatment. It is hoped that the safety tolerability and the value of dose selection will be demonstrated in this healthy volunteer study, with sufficient safety data generated to enable dose selection for larger and more definitive Phase 2 studies.

3. STUDY OBJECTIVES AND ENDPOINTS

Primary Objective	Primary Endpoint
To assess safety and tolerability of CX-4945 administered orally 200mg QD, 200mg BID and 400mg BID for continuously 5 days to healthy subjects	To evaluate the adverse events occurring from Day 1 to Day 5 (including vital signs, physical findings, clinical laboratory, and ECG results) as characterized by type, frequency, severity [as graded by the National Cancer Institute Common Terminology Criteria for Adverse Events [CTCAE] version 5.0], timing, seriousness, and relationship to study therapy after administration of 200mg QD, 200mg BID and 400mg BID for continuously 5 days to healthy subjects
Secondary Objectives	Secondary Endpoints
To evaluate changes in blood chemistry and other health assessment	Changes in blood chemistry and other health assessment from Day 1, Day 3, Day 5, and Day 6 morning.

4. STUDY DESIGN

4.1. OVERALL DESIGN

This is a phase I single center, open-label, parallel design in 30 subjects to evaluate safety and tolerability of CX-4945 200mg QD, 200 mg BID and 400mg BID doses (10 subjects in each regimen) for continuously 5 days in healthy subjects for dose selection. Up to approximately 30 subjects will be enrolled into this study. A screening evaluation will occur within 28 days prior to Day 1. A subject screening number will be assigned to each subject in successive order of consent signing, beginning with S001. At the end of screening all qualified subjects will be assigned sequentially to following three treatment cohorts:

- **Cohort 1:** CX-4945 200mg QD
- **Cohort 2:** CX-4945 200mg BID
- **Cohort 3:** CX-4945 400mg BID

A subject number will be assigned to participants when they have confirmed eligible for the study on Day1. Each cohort will receive a unique numeric designation, and will precede the subject number (e.g. at cohort 1 the first two subjects would be 01-001 and 01-002; at cohort 2 the first two subjects would be 02-001 and 02-002).

The total duration of the treatment will be 5 days. Subjects will be followed up at 14 days from the start of the treatment. The total duration for each subject in the study (including the screening) will be up to 42 days.

4.2. JUSTIFICATION FOR DOSE

A series of ten horizontal black bars of varying lengths, decreasing in length from top to bottom. The bars are evenly spaced and extend across the width of the frame.

4.3. STUDY STOPPING CRITERIA

During the study, serious adverse events will be reviewed by the sponsor as they are reported from the investigational center to identify safety concerns. The study may be terminated by the sponsor at any time.

At any time during the study and after discussion between the sponsor medical officer, medical monitor and investigator, the study may be stopped or terminated if the following occur:

1. Previously unknown data that raise concern about the safety of the study participants become available
2. Three or more subject have experienced a clinical laboratory AE of Grade 3 or higher determined to be possibly or probably related to CX-4945.

4.4. END OF STUDY DEFINITION

A subject is considered to have completed the study if he or she has completed the Treatment Phase and Follow-up visits (Days 14).

Discontinuation from CX-4945 does not mean the withdrawal from the study assessments. Subjects who discontinued therapy should remain in the study and continue follow-up for key outcomes. The only reasons for end of study are withdrawal of consent and loss to follow-up,

5. STUDY POPULATION

This study will enroll up to approximately 30 healthy normal volunteers. All qualified subjects will be assigned sequentially to three treatment cohorts, CX-4945 200mg QD, 200 mg BID and 400mg BID doses and be hospitalized for 6 days treatment.

5.1. SUBJECT ELIGIBILITY CRITERIA

This study can fulfill its objectives only if appropriate subjects are enrolled. The following eligibility criteria are designed to select subjects for whom participation in the study is considered appropriate. All relevant medical and nonmedical conditions should be taken into consideration when deciding whether a particular subject is suitable for this protocol.

5.1.1. Inclusion Criteria

Subjects must meet all of the following inclusion criteria to be eligible for enrollment in the study:

1. Healthy male and female subjects 20 to 55 years of age, inclusive, at screening
2. Body mass index (BMI) within the range of 18.0 to 30.0 kg/m², inclusive, and a minimum weight of 50.0 kg at screening
3. Subjects who are of reproductive potential agreed to remain abstinent or use (or have their partner use) an acceptable method of birth control (intrauterine device, hormonal contraception, vasectomy or condom) from screening until at least 2 weeks after the last study drug administration.
4. Physically and mentally healthy subjects as confirmed by an interview, medical history, clinical examination, and electrocardiogram;
5. Subject with acceptable hematology, biochemistry and urinalysis during screening period.
6. Subject is willing and able to comply with study procedures and sign informed consent.

5.1.2. Exclusion Criteria

Potential subjects meeting any of the following criteria will be excluded from participation in this study:

1. Pregnant or nursing women.

NOTE: Women of child-bearing potential and men must agree to use adequate contraception (hormonal or barrier method of birth control; or abstinence) prior to study entry and from screening until at least 2 weeks after the last study drug administration. Should a man father a child, or a woman become pregnant or suspect she is pregnant while participating in this study, he or she should inform the treating physician immediately.

2. Active or uncontrolled infections such as COVID-19, HIV or with serious illnesses or medical conditions which would not permit the subject to receive study treatment.
3. Subject has received any prescription of drug within 3 days prior to study enrollment.
4. Subject has drug abuse history.
5. Any active or recurring clinically significant hepatic disease including HBV and HCV.
6. Subject has received any investigational agent within 28 days or 5 half-lives, whichever is longer, prior to the first dose of investigational product.
7. Any other medical reason as determined by the investigator.

5.2. SCREEN FAILURES

All subject who fail to meet eligibility criteria are considered screen failures, and are exited from the study. Screening number, demographics and reason for screen failure will be recorded.

If a subject initially fails to meet inclusion/exclusion criteria and is later reconsidered for participation, the subject will be re-consented and assigned a new unique identification number at the time of re-screening and may be enrolled if they are found to meet all inclusion and no exclusion criteria at the subsequent screening visit.

5.3. SUBJECT REPLACEMENT

All subjects who are removed from the study for any reason other than for adverse events (e.g., voluntary discontinuation at the subjects request, or a severe violation of the study protocol) will be replaced. Data from these removed subjects will be included in the overall safety analysis. If subject completed the treatment (Day1 to Day5) but not finished the Day 14 follow up visit, the subject will not be replaced.

6. STUDY TREATMENT

6.1. STUDY TREATMENT ADMINISTRATION

6.1.1. Investigational Drug Product Description

For this study, the investigational product is CX-4945 that will be assigned to the three cohorts.

Refer to the Investigator's Brochure for more information.

6.1.2. Dosing and Administration of CX-4945

Subject enrolled to the treatment cohort 1 will receive 200 mg of CX-4945 QD by mouth, beginning on Day 1, and continuously through Day 5. The cohort 2 and cohort 3 will receive 200 mg and 400mg of CX-4945 BID by mouth, beginning on Day 1, and continuously through Day 5.

Other oral medications should be taken at least one hour before or 2 hours after ingesting the dose of CX-4945 capsules.

Subjects will take 1-2 200-mg CX-4945 capsules, two hours after the morning meal and two hours after the evening meal (dinner) with water. Subjects are advised to take 1 capsule at a time with a pause in between each. This method may prevent a clumping effect in the stomach, so a subject can take as much as 10 minutes to swallow each capsule.

CX-4945 will be taken on an empty stomach with at least six ounces (180 mL) of water. After CX-4945 administration, the subject will be NPO (except for water) for 2 hours, after which, the subject may eat.

Subject will take 3 meals a day provided by hospital. If any reason to have an extra food should be approved by investigator. Subjects are not allowed to smoke during the 5 days treatment.

6.1.3. CX-4945 Compliance

Site staff will dispense CX-4945 to the subjects assigned to the cohort 1, 2 or 3. The site staff will make sure that the subject will take the IP properly. Any missed doses or non compliance should be documented in the dosing record form. The IP will be counted, documented, and recorded by site staff.

6.1.4. CX-4945 Dose Discontinuation

The most common drug related adverse events reported for CX-4945 are predominantly gastrointestinal disorders, including nausea, vomiting and diarrhea. Treatment with CX-4945 can be discontinued prematurely due to the following reasons:

- Subject have experienced a clinical laboratory AE of Grade 2 or higher determined to be possibly or probably related to CX-4945
- Withdrawal from the study treatment or participation
- Pregnancy
- Lost to follow-up
- Reported major protocol deviations, as determined by the Investigator or the Sponsor
- Subject is treated with or takes a prohibited medication.
- If any clinical adverse event, laboratory abnormality, or other medical condition or situation occurs that continued treatment under the protocol would not be in the best interest of the subject.

Discontinuation from CX-4945 does not mean the withdrawal from the study assessments. Subjects who discontinued therapy should remain in the study and continue follow-up for key outcomes. The only reasons for end of study are withdrawal of consent from study participation and loss to follow-up.

6.2. INVESTIGATIONAL PRODUCT SUPPLIES, STORAGE AND ACCOUNTABILITY

6.2.1. Investigational Product Supplies

CX-4945 will be supplied by Senhwa Biosciences. Study sites will receive CX-4945 prior to enrollment of the first subject. The clinical site pharmacy /qualified staff member will dispense the supplies to the subject enrolled to the cohort 1 to 3 in quantities appropriate according to the study visit schedule. Any unused product or waste material should be disposed of in accordance with local requirements.

[REDACTED]

6.3. CONCOMITANT MEDICATION

Investigators should always manage their subjects according to their medical judgement based on the particular clinical circumstances. Any drug contain ingredient of activated charcoal (such as Norit) are prohibited for 14 days during the study.

[REDACTED]

[REDACTED]

7. STUDY COMPLETION OR DISCONTINUATION

7.1. SUBJECT COMPLETION

A subject is considered to have completed the study if he or she has completed the treatment phase and Follow-up visits at Day 14.

Discontinuation from CX-4945 does not mean the withdrawal from the study assessments. Subjects who discontinued therapy should remain in the study and continue follow-up for key outcomes. The only reasons for end of study are withdrawal of consent from further participation in the study and loss to follow-up.

7.2. SUBJECT WITHDRAWAL FROM PARTICIPATION IN THE STUDY

At any point during the study all subjects have the right to withdraw consent from further participation in the study refusing to complete scheduled study assessments and follow-ups without prejudice to future care. If the subject refuses further visits, the subject should continue to be followed unless the subject withdraws consent for disclosure of future information or for further contact. In this case, no further study-specific evaluations should be performed and no additional data should be collected. The sponsor/investigator may retain and continue to use any data collected before such withdrawal of consent.

Another reason for withdrawal from study is loss to follow-up. Before a subject is identified as lost-to-follow up, the site should make all reasonable efforts to contact the subject. These attempts must be documented and should include at a minimum one phone call and one certified letter.

The reason for withdrawal from the study will be recorded in the subject medical records.

7.3. SUBJECT DISCONTINUATION FROM STUDY TREATMENT

Subjects may withdraw from treatment at any time at their own request, or they may be withdrawn at any time at the discretion of the investigator/sponsor for safety or behavioral reasons, or the inability of the subject to comply with the protocol-required schedule of study visits or procedures at a given investigator site.

All subjects who discontinued from study treatment but maintain consent, should remain in the study through the end of the study period for all important safety assessments.

Investigators considering subject withdrawal from study treatment should contact the medical monitor prior to such discontinuation. Subjects who have study treatment discontinued will continue to be followed, per protocol, whenever possible. If visits to the site are not possible, subjects can be followed via telehealth or other approaches (telephone calls, e-mails, and texts to ascertain vital status in all subjects.

Subjects who have study treatment discontinued due to a serious adverse event will be followed until study completion, resolution or stabilization of the event (whichever occurs later).

Reasons for withdrawal of study treatment may include:

- Subject refused further
- Pregnancy
- Unacceptable toxicity
- Significant study therapy non-compliance
- If any clinical adverse event (AE), laboratory abnormality, or other medical condition or situation occurs such that continued participation in the study would not be in the best interest of the participant
- If the participant meets an exclusion criterion (either newly developed or not previously recognized) that precludes further study participation

8. STUDY ASSESSMENTS AND PROCEDURES

The study will have three phases: Screening Phase/Visit, Treatment Phase, and Follow-Up Phase. A schedule of assessments and procedures is provided in **Section 1.3**.

8.1. STUDY PROCEDURES

8.1.1. Screening Period:

The subject will sign and date the informed consent form (ICF) prior to any study-related procedures. The study center will maintain the study-specific screening and enrollment logs at their site.

For screening procedures see the Schedule of Activities in **Section 1.3** and Assessments in **Section 8.2**.

8.1.2. Treatment Period:

For the treatment period procedures see the Schedule of Activities **in Section 1.3** and Assessments in **Section 8.2**.

Subjects who fulfill all the entry criteria and have written informed consent will be enrolled to the study. Enrollment is specifically referred to the visit of treatment on Day 1. All subjects will be 5-days hospitalized during treatment period. Clinical visit will be scheduled to occur at the intervals indicated as Table 1. After confirming satisfaction of check-in procedure, the subjects will be assigned a subject number and will have completed the following evaluations and assessments on Day 1 prior to treatment: review of any changes in medication history, physical examination, vital signs, clinical status –laboratory sample collection for routine serum biochemical, hematologic, coagulation analysis.

Eligible subjects will be assigned to one of cohort groups to receive the study drug. Considering a ~15% screen failure rate, approximately 45 subjects will be screened in order to recruit 30 evaluable subjects.

During the treatment phase, subjects assigned to the cohort 1 will receive CX-4945 (200 mg) once a day for up to 5 days. For cohort 2, subjects will receive CX-4945 (200 mg) twice a day for up to 5 days. For cohort 3, subjects will receive CX-4945 (400 mg) twice a day for up to 5 days.

Details on CX-4945 administration can be found in **Section 6**.

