9.3. SAMPLE SIZE DETERMINATION AND RATIONALE

A total of 30 subjects will be assigned sequentially into 3 cohorts in this study. The sample size is based on clinical judgment. No statistical power calculation is used to establish the sample size for this proof-of-concept study.

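### Does a screen-failure rate of about 15% justify screening about 45 subjects to obtain 30?

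*Protocol*

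**What the plan says.** Protocol section 8.1.2 (Treatment Period, under 8.1 Study Procedures) gives the recruitment assumption in one sentence: "Considering a ~15% screen failure rate, approximately 45 subjects will be screened in order to recruit 30 evaluable subjects".

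The target of 30 recurs elsewhere. Section 4.1 has "Up to approximately 30 subjects will be enrolled into this study", with 10 subjects per regimen. Section 9.3 has "A total of 30 subjects will be assigned sequentially into 3 cohorts in this study" and adds "No statistical power calculation is used to establish the sample size for this proof-of-concept study". SAP section 4.3 repeats section 9.3.

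Two further sections bear on how many people might need screening:

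- Section 5.2 defines the loss that the rate refers to: "All subject who fail to meet eligibility criteria are considered screen failures, and are exited from the study". It also allows re-screening under a new number.
- Section 5.3 provides for replacement and covers "All subjects who are removed from the study for any reason other than for adverse events".

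Neither section gives a rate or refers to the 45. The SAP states no screening number and no screen-failure rate. The word evaluable is not defined in either document, and the named analysis populations are ITT, PP and Safety.

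**The concern.** The sentence reads as a calculation: a rate, a target, and a screening number that should result from them. It does not result from them. A reader cannot tell whether the planner assumed about 15% failure, about 33% overall loss, or about 15% plus an allowance that is not written down.

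These readings point in different directions. If 15% is right and is the only loss, 45 is more healthy volunteers than are needed. If the overall loss is really about one third, 45 is barely enough on average and could easily fall short. For a single-center study planned to last 5 months, a site or ethics committee might want to know which applies.

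**Working it through.** **Inputs.** Target 30 (protocol sections 4.1 and 9.3); failure rate about 15% and screening number about 45 (protocol section 8.1.2). No other loss rate is given anywhere.

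**Attempt to reproduce 45.**

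- Usual formula, target/(1 − rate): 30/0.85 = 35.3, so 36.
- Cruder formula, target × (1 + rate): 30 × 1.15 = 34.5, so 35.
- Rate taken as 10%: 30/0.90 = 33.3, so 34.
- Rate taken as 20%: 30/0.80 = 37.5, so 38.

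None of these reaches 45. The excess over 36 is 9 subjects, and 9/36 = 25%, which is more than rounding.

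**Working back from 45.**

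- Overall loss implied: 1 − 30/45 = 33.3%.
- Expected eligible at 15% failure: 45 × 0.85 = 38.25, about 8 above the target.

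**Is 45 enough?** Treat screenings as independent with a constant failure rate (an assumption), so that the number eligible is binomial. The probability of at least 30 eligible is:

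| Screened | 15% failure | 20% failure |
|---|---|---|
| 36 | 0.710 | 0.401 |
| 40 | 0.970 | 0.839 |
| 45 | 0.9995 | 0.989 |

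Screening the expected number, 36, would miss the target in about 29% of cases at 15% failure. Some margin above 36 is therefore sensible, and 45 provides one that still holds at 20%.

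**Could later losses account for 45?** Suppose a further fraction of subjects who pass screening is lost. This is an illustration, as the documents give no such rate. The probability of still having 30 from 45 screened, at 15% failure, is:

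- 5% further loss: success rate 0.85 × 0.95 = 0.8075, probability 0.992.
- 10% further loss: success rate 0.85 × 0.90 = 0.765, probability 0.954.

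So 15% failure, a 10% later loss and roughly 95% assurance lead to 45. If instead the overall loss were truly 33.3%, 45 screened would give at least 30 with probability of only 0.57. The back-calculated 33% is therefore a poor candidate for what the planner assumed, and a poor replacement figure.

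**The case for a change.** The best case for a correction is that the sentence names screen failure and nothing else, and 45 is out of reach of 15% by any rounding. A margin, replacements and re-screens are possible explanations, but the protocol attaches none of them to the 45 and gives no rate for any. Sections 4.1 and 9.3 treat 30 as the number enrolled or assigned, so they do not support a stricter count of evaluable subjects. One added clause would settle the matter at almost no cost.

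The arithmetic in this stands: 45 does not follow from 15% alone, and the reason for the difference is not documented. What does not stand is the step from there to an error. The wording is approximate throughout and fits a rounded planning ceiling that takes screen failure into account.

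The protocol also has points where someone who passed screening can still drop out: the negative COVID-19 test required before admission (Schedule of Activities, note 10), the Day 1 pregnancy test (section 8.2.1.1), a screening window of up to 28 days, and the replacement rule in section 5.3. Some Day 1 failures might themselves be counted as screen failures under section 5.2, so how much these add is unknown.

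Any specific replacement number would also rest on the critic's own choice. About 40 needs an assurance level that the protocol does not state, and about 33% would make 45 look inadequate.

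**Conclusion.** The mismatch is real but calls for no change. At 15% failure the expected requirement is 36 against a stated 45, a difference of 9 planned screenings. The documents do not show which figure, if either, is wrong, and the plan works as written: 45 screened is ample at 15% failure and still ample at 20%.

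Nothing downstream uses the figure. Screening can stop once the cohorts are full, so 45 need not be reached. The 30 subjects rest on clinical judgment with no power calculation, section 9.7.4 plans no inferential statistics, and the SAP contains neither 15% nor 45. Correcting the sentence would tidy the record of a recruitment assumption without altering who is enrolled, what is analysed or what is concluded.

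This rests on the independence and constant-rate assumption behind the probabilities, and on the site stopping screening at full enrolment. The protocol does not spell out the latter, but its enrolment limit of about 30 implies it.
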